6.2.4 Data handling

The details for data handling will be provided in Appendix 1. Calculation of duration, imputation of missing or partial start and stop dates of adverse events and concomitant medications and handling of inexact values are described.

6.2.5 Individualized Neuromuscular Quality of Life (INQoL)

The calculation of the INQoL questionnaire scores is detailed in Appendix 2.

6.2.6 Study Visits

Nominal visits will be used as the analysis visits for subjects who were randomized to deflazacort under protocol version 3.0 or enrolled under protocol version 4.0.

For subjects who were randomized to placebo under protocol version 3.0 and then reconsented to receive deflazacort under protocol version 4.0, the nominal visits will be remapped to have the start of the open label visit as the first analysis visit. For example:

Nominal visit for placebo subjects	Analysis visit
V1	
V2	
V3 (Start of open label)	V1
V4	V2

QMD Ref: Worldwide-TMP-ST-005-7.0 Effective: 12Aug2019	Governing QMD: Worldwide-SOP-ST-001
Confidentiality Statement	
This document is the property of Worldwide Clinical Trials Inc. and may not be duplicated, copied, altered or removed from company without prior approval from Worldwide Quality Assurance or in compliance with Worldwide Standard Operating Procedures.	

Worldwide Clinical Trials Controlled Quality Management Document		
 WORLDWIDE CLINICAL TRIALS	Sponsor:	PTC Therapeutics, Inc
	Protocol Number:	PTCEMF-GD-004
STATISTICAL ANALYSIS PLAN		

V5	V3
...	...

All summaries will be based on analysis visits. Assessment taken under unscheduled visits or nominal visits during the placebo period for subjects who randomized to placebo group will be presented in the subject listings only.

6.2.7 Change from Baseline

Change from baseline for any variable at a given visit will be calculated by subtracting the baseline value (last non-missing scheduled, unscheduled or repeat value before the first dose of deflazacort) of the variable from the value of the variable at the given visit. If there is no baseline or screening value, then the change from baseline will be missing.

6.3 Conventions

All data listings, summaries, figures, and statistical analyses will be generated using SAS version 9.4 or higher¹.

Summary displays based on the Enrolled Population will have Overall as the column header. In all summary tables, all subjects who received at least one dose of deflazacort will be pooled regardless of the protocol versions they were enrolled, and the treatment column will be displayed as Deflazacort. Deflazacort treated subjects will be pooled in all safety summaries across all deflazacort treated periods.

The following defined study period will be presented in the by-subject listings only:

- Placebo period: The observations before entering to open label for subjects randomized to placebo under protocol version 3.0.

Listings will be sorted in the following order parameter, subject and visit (sorted in chronological order – earliest to latest) unless otherwise stated. The appropriate study period will be included in the listings.

Continuous variables will be summarized by the number of non-missing observations, mean, median, standard deviation, and minimum and maximum. For the primary and secondary efficacy endpoints, the lower and upper 95% confidence limits for the mean will be provided.

QMD Ref: Worldwide-TMP-ST-005-7.0 Effective: 12Aug2019	Governing QMD: Worldwide-SOP-ST-001
Confidentiality Statement	
This document is the property of Worldwide Clinical Trials Inc. and may not be duplicated, copied, altered or removed from company without prior approval from Worldwide Quality Assurance or in compliance with Worldwide Standard Operating Procedures.	

Worldwide Clinical Trials Controlled Quality Management Document		
 WORLDWIDE CLINICAL TRIALS	Sponsor:	PTC Therapeutics, Inc
	Protocol Number:	PTCEMF-GD-004
STATISTICAL ANALYSIS PLAN		

Categorical variables will be summarized by percentage and frequency counts. Percentages will be based on the number of non-missing observations or the subject population unless otherwise specified. For each variable, all categories will be shown.

6.3.1 Decimal Places

Means, medians and percentiles will be displayed to one more decimal place than the data, dispersion statistics (e.g. standard deviation) will have two more decimal places, and the minimum and maximum will be displayed to the same number of decimal places as reported in the raw data. Percentages will be displayed with one decimal place.

6.4 Subject Disposition

Subject disposition will be summarized as follows:

- The number of subjects, who entered the study under protocol v3.0, who entered the study under protocol v4.0, who entered the open label, were randomized under protocol v3.0, who were transitioned to the open label by previous treatment received and overall, who received at least 1 dose of study drug and who are in each analysis set will be summarized for the Enrolled Population.
- The number of subjects screened, and the number of subjects who had screening failed. The number of subjects who prematurely discontinued study drug and the discontinuation reason will be tabulated for the Safety Population.

6.5 Protocol Deviations

Protocol deviations including those related to COVID-19 will be presented in the subject listings only.

6.6 Demographics and Baseline Characteristics

Demographic data and baseline characteristics will be summarized for the Safety Population. Demographic data, age in years at informed consent, sex, race (American Indian or Alaska Native; Asian; Black or African American; Native Hawaiian or Other Pacific Islander; White), as well as height in cm, weight in kg, body mass index (BMI) in kg/m² at screening and duration of clinical symptom and left ventricular ejection fraction (%) from Echocardiogram and FKRP Genotyping will be summarized. Where patients have checked more than one box for race, they will be presented in the demography summary as “Multiple Race”. The listing will document all selected races.

QMD Ref: Worldwide-TMP-ST-005-7.0 Effective: 12Aug2019	Governing QMD: Worldwide-SOP-ST-001
Confidentiality Statement	
This document is the property of Worldwide Clinical Trials Inc. and may not be duplicated, copied, altered or removed from company without prior approval from Worldwide Quality Assurance or in compliance with Worldwide Standard Operating Procedures.	

Worldwide Clinical Trials Controlled Quality Management Document		
 WORLDWIDE CLINICAL TRIALS	Sponsor:	PTC Therapeutics, Inc
	Protocol Number:	PTCEMF-GD-004
STATISTICAL ANALYSIS PLAN		

6.7 Medical History

Medical history conditions will be presented for the Safety Population. Conditions will be presented by Medical Dictionary of Regulated Activities (MedDRA, version 23.1) primary system organ class and preferred term.

Medical history will be presented in the by-subject listings only.

6.8 Prior and Concomitant Medications

Prior and concomitant medications will be coded using the version of World Health Organization Drug Dictionary (WHODrug Global B3 version Sep 2020) into Anatomical-Therapeutic-Chemical (ATC) classification codes.

Medications will be classified as prior medications, and/or concomitant medications. Any medication used prior to the first dose of deflazacort will be classified as prior medication and those used on or after first dose of deflazacort date until the date of last dose of deflazacort will be classified as concomitant medications. Medications used prior to the first dose and continued during deflazacort treatment will be considered as both prior and concomitant medication.

Prior and concomitant medications will be presented in the by-subject listings only.

6.9 Exposure to Study Drug

Deflazacort treatment duration (days) is defined as the date of last deflazacort dose before tapering – the date of first deflazacort dose +1. The deflazacort treatment duration will not consider breaks in therapy.

Exposure will be summarized in all deflazacort treated subjects across all deflazacort treated periods using Safety Population.

Placebo treatment duration (days) is defined as the date of last placebo dose – the date of first placebo dose +1. Placebo treatment duration will only be presented in the by-subject listings.

6.10 Efficacy Analyses

All efficacy analyses of data will be performed using the Full Population. All data will be summarized at scheduled visits. All data, including unscheduled visit data, will be presented in the by-subject listings.

Efficacy will be summarized by visit for the period treated with deflazacort.

QMD Ref: Worldwide-TMP-ST-005-7.0 Effective: 12Aug2019	Governing QMD: Worldwide-SOP-ST-001
Confidentiality Statement	
This document is the property of Worldwide Clinical Trials Inc. and may not be duplicated, copied, altered or removed from company without prior approval from Worldwide Quality Assurance or in compliance with Worldwide Standard Operating Procedures.	

Worldwide Clinical Trials Controlled Quality Management Document		
 WORLDWIDE CLINICAL TRIALS	Sponsor:	PTC Therapeutics, Inc
	Protocol Number:	PTCEMF-GD-004
STATISTICAL ANALYSIS PLAN		

The data collected before start of deflazacort for subjects receiving placebo under protocol version 3.0 will be included in the by-subject listings only.

6.10.1 Analysis of Primary Endpoint

The actual value and the change from baseline in 4-stair climb time, measured in seconds will be summarized descriptively (number of non-missing observations (n), mean, standard deviation, minimum, median, and maximum) at each assessment visit for the Full Population. The time to climb 4 stairs is performed twice at each visit. The maximum value at each visit will be used for summary and analysis purposes.

In addition, the 95% confidence interval for the mean change from baseline after 26 weeks of deflazacort treatment will be provided.

A waterfall plot of the change in 4- stair climb time at Week 26 will be provided.

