### 4.1 Overview

### 4.2 Inclusion Criteria

1. Genetic diagnosis of LGMD2I (confirmed mutation in the FKRP gene)
2. Male and female subjects aged  $\geq 18$  years
3. Ability to ascend 4 stairs  $\geq 2.5$  seconds and be able to complete the ascent and descent both at screening and baseline
4. Ability to understand the nature of the study and the consent form and to comply with study related procedures
5. Must weigh  $\geq 35$  to  $\leq 112.5$  kg

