## **9 STATISTICAL CONSIDERATIONS**

### **9.1 Statistical Hypothesis**

No hypothesis will be tested in this study.

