This document is the property of Worldwide Clinical Trials Inc. and may not be duplicated, copied, altered or removed from company without prior approval from Worldwide Quality Assurance or in compliance with Worldwide Standard Operating Procedures.	

Worldwide Clinical Trials Controlled Quality Management Document

Sponsor: PTC Therapeutics, Inc

Protocol Number: PTCEMF-GD-004

STATISTICAL ANALYSIS PLAN

Subjects Randomized to Placebo Prior to 01 February 2020	Subjects will have the option to be consented under Version 4.0 and immediately accelerated to the Week 26 visit and begin the open label study.
Subjects Randomized to Deflazacort Prior to 01 February 2020	Subjects will return to the clinic at their scheduled Week 26 Visit under Version 3.0. At the Week 26 visit, the subject will undergo Week 26 procedures and have the option to re-consent under Protocol Version 4.0 and continue for an additional 26 weeks in the open label period.
Subjects Randomized to Placebo AFTER 01 February 2020	Subjects will have the option to be consented under Protocol Version 4.0 and begin at the Week 26 Visit (Open-label period).
Subjects Randomized to Deflazacort AFTER 01 February 2020	Subjects will have the option to be consented under Protocol Version 4.0 at their Week 13 Visit. These subjects will be provided the option to re-consent to the study under Protocol Version 4.0 at Week 13 and continue until Week 26. After Week 26, the subjects will be ineligible to continue for the additional 26 weeks of open label treatment.
New subjects enrolled until 31 May 2020	Subjects will have the option to be consented under Protocol Version 4.0 and perform Baseline through Week 26 visit procedures. These subjects will be assigned deflazacort in an open-label fashion. After Week 26, the subjects will be ineligible for the additional 26 weeks of the trial.

On 23rd July 2020, a PTC corporate decision was made to terminate the study early due to the slow recruitment and company’s strategy change. This decision is not related to the safety or efficacy of the study drug. Due to the early termination, only 11 subjects were enrolled in this study.

QMD Ref: Worldwide-TMP-ST-005-7.0 Effective: 12Aug2019

Governing QMD: Worldwide-SOP-ST-001

Confidentiality Statement

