4 SAMPLE SIZE

This is a single arm, open label study to evaluate the efficacy and safety of deflazacort in subjects with LGMD2I. The primary endpoint is the change in 4-stair climb in seconds after 26 weeks of treatment.

Sample size is based on assuming the deflazacort can prevent subjects' further progression within 6 months i.e. the mean change of 4-stair climb after 26 weeks of treatment is 0 second and the standard deviation of the change is 0.7, with a total of 30 subjects, the 95% confidence will be from -0.25 to 0.25 seconds.

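### The plan gives no value to a subject who becomes unable to climb after baseline, so such a subject would fall out of the Week 26 mean and bias it favourably

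*SAP*

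**What the plan says.** The primary endpoint is the change from baseline in time to climb 4 stairs after 26 weeks of treatment. SAP Section 6.10.1 summarises it by "number of non-missing observations (n), mean, standard deviation, minimum, median, and maximum" and continues: "In addition, the 95% confidence interval for the mean change from baseline after 26 weeks of deflazacort treatment will be provided". The Week 26 changes are also to be shown in a waterfall plot. Protocol Section 9.5.6 specifies the same summary and interval. The test is done twice per visit and the larger (slower) time is used, which needs at least one recorded time.

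The ability to do the test is an entry condition only. Under inclusion criterion 3 (Protocol Section 4.2) a subject must "be able to complete the ascent and descent both at screening and baseline". Nothing comparable applies at Week 26.

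The rules on missing data do not cover this case:

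- SAP Section 6.2.7 deals with a missing baseline, not with a Week 26 time that cannot be obtained.
- SAP Section 6.2.4 and Appendix 1 deal with durations, dates of adverse events and medications, and inexact values. A result recorded as greater than x is analysed as x, but no x is defined for a failed climb.
- Neither document has a time cap, a worst-value rule, a rank or rate analysis, or a count of subjects unable to climb.

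SAP Section 6.10.2 summarises stair descent, up-and-go and the 10 m run/walk in the same way as the primary endpoint.

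**The concern.** The endpoint is meant to show progression, and the most extreme progression yields no number. Protocol Section 1.1 describes a progressive disease that can include loss of ambulation, and Protocol Section 7.2 lists clinically significant worsening as a reason for leaving the study. A missing Week 26 time may therefore be missing because of the outcome itself.

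If that happens, the mean is taken over those who can still climb. The estimate is too favourable: it shows less worsening, or more improvement, than the treated group had. The study is a single arm and placebo-period data are only listed, so no comparison group carries the same loss. With few subjects, each one weighs heavily in the mean. Taking the slower of two attempts does not help, because a failed attempt has no time: if one attempt fails, the completed one is used, and if both fail there is nothing to use.

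**Working it through.** **Inputs from the documents.** SAP Section 4 assumes that "the mean change of 4-stair climb after 26 weeks of treatment is 0 second" and that "the standard deviation of the change is 0.7, with a total of 30 subjects", and concludes that "the 95% confidence will be from -0.25 to 0.25 seconds". SAP Section 1 reports that "only 11 subjects were enrolled in this study".

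**Assumptions, not in the documents.** One of 11 subjects is unable at Week 26 (k = 1). The change c assigned to that subject is +2, +5 or +10 s. The other ten have mean change 0 and SD 0.7 s. All 11 are taken as treated and due at Week 26; with fewer, each subject would weigh more.

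**Step 1: the plan's own figure.** Half-width = 1.960 × 0.7 / √30 = 0.2505 s, which reproduces ±0.25. The plan used the normal quantile; the t quantile gives 0.261. With 11 subjects the half-width is 0.41 s (normal) or 0.47 s (t).

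**Step 2: direction.** Let the ten observed subjects have mean m. Omitting the eleventh reports m; including that subject gives (10m + c)/11. The difference is (c − m)/11, which is positive whenever the omitted subject did worse than the rest. Omission therefore always favours the drug. It moves the mean toward zero only if the full-group change is a worsening.

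**Step 3: size.** With m = 0 the mean including the subject is M = c/11. The combined SD is √{[9 × 0.7² + 10 × M² + (c − M)²]/10}, and the interval uses t on 10 df.

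| Handling | Mean change (s) | SD | 95% interval |
|---|---|---|---|
| Omitted (n = 10) | 0.00 | 0.70 | −0.50 to 0.50 |
| Included, c = +2 | 2/11 = 0.18 | 0.90 | −0.42 to 0.78 |
| Included, c = +5 | 5/11 = 0.45 | 1.65 | −0.65 to 1.56 |
| Included, c = +10 | 10/11 = 0.91 | 3.09 | −1.17 to 2.98 |

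With two of 11 unable the means are 0.36, 0.91 and 1.82 s. With one of the planned 30 they are 0.07, 0.17 and 0.33 s.

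**Step 4: how much it takes.** One omitted subject moves the mean by the planned half-width when c = 0.25 × 11 = 2.75 s. At 30 subjects it would take 0.25 × 30 = 7.5 s.

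**Step 5: velocity scale.** Velocity is 4/time, and inability is 0, so no cap has to be chosen. A subject with an 8 s baseline goes from 4/8 = 0.5 stairs/s to 0, which shifts a mean of 11 by −0.5/11 = −0.045 stairs/s. The fastest baseline allowed is 2.5 s, or 4/2.5 = 1.6 stairs/s, so one subject's contribution cannot exceed 1.6/11 = 0.145 stairs/s.

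**The case against.** The strongest reply is that the plan is silent and contains no exclusion rule. A reader might infer that it deliberately excludes such subjects, and the text does not support that. They stay in the Full Population and in the by-subject listings (SAP Section 6.10). The number of observations is shown at each visit, and reasons for stopping study drug are tabulated (SAP Section 6.4). Test conduct is described in a separate manual that was not available. It may set a code or a maximum time, and a result entered as greater than x would be analysed as x. This stands as a limit on the point. But neither document brings in such a code, and a smaller n does not tell the reader why a time is missing.

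Other stronger readings also go too far:

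- **Slow climbers enter without limit.** Criterion 3 has no upper time, but footnote 12 of the schedule of events (both documents) requires at most 8 seconds at screening and baseline. The two must be reconciled. The gap exists under either, because an entry limit does not prevent later loss of ability.
- **The bias always points to no progression.** It points in the favourable direction, and if the others improve it exaggerates improvement.
- **The bias is 1 to 2 s.** Going from 8 s to an assumed cap of 20 or 30 s gives 12/11 = 1.09 or 22/11 = 2.0 s. No cap appears in the documents, and those changes are 17 to 31 times the planned SD (12/0.7 and 22/0.7).
- **One subject decides the answer.** Protocol Section 9.1 states: "No hypothesis will be tested in this study". No decision is there to flip; what suffers is an estimate and its interval.
- **Any missing Week 26 time is informative.** Study termination and missed visits also leave times missing, for reasons unrelated to ability.

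**Conclusion.** The point holds in a conditional form. Followed as written, and unless the test manual supplies a code, the plan drops disease-caused inability from the Week 26 mean, interval and waterfall plot, and the result is then too favourable. For one subject in 11 the understatement is about 0.18 to 0.91 s over assumed changes of +2 to +10 s. That is somewhat below to well above the planned half-width of 0.25 s. These figures rest on assumed values of k and c and on the other ten averaging zero. No document says that any subject lost the ability, so the actual bias may be nil. Type I error and power are not at issue. This is a cheap improvement to the plan and does not invalidate the primary summary.

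**What to change.** Keep time in seconds as the primary summary and add the following:

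1. Beside the Week 26 mean, report the number of subjects unable to complete the climb because of disease. Count separately the times missing for other reasons, such as study termination or missed visits. If nobody was unable, a stated zero makes the primary result more credible.
2. Show subjects unable because of disease at the worst end of the waterfall plot, marked as such.
3. Add a supportive summary of stair-climb velocity, 4/time, with 0 for those unable.
4. Do the same for stair descent (4/time), the 10 m test (10/time) and up-and-go (1/time).
5. If the test manual already defines a code or maximum time for a failed attempt, cite it in the SAP and state how it is analysed.
6. Reconcile the upper time limit between inclusion criterion 3 and footnote 12.

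The cost is about four small supportive tables, a plotting rule and a recorded reason for each missing time. There are two drawbacks. Readers have a second scale to follow. Assigning the reason also calls for judgement in an open-label study, so it should rest on what the site recorded at the visit and be settled before the summaries are produced.

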6.10.2 Analysis of Secondary Endpoints

The following secondary endpoints will be summarized similar to the primary endpoint by study visits for the actual value and the change from baseline.

- Forced vital capacity (FVC)
- 2-minute walk test
- Time to up and go
- Time to descent 4 stairs
- Time to run/walk 10 meters
- Maximal inspiratory pressure (MIP)
- Maximal expiratory pressure (MEP)
- Hand-held myometry

For all endpoints with repeated measurements, the maximum value at each visit will be used for summary and analysis purposes.

Similar as the primary endpoint, summary statistics such as n, mean, standard deviation, median, minimum and maximum, and the 95% confidence interval for the mean change at Week 26 will be provided for all secondary endpoints.

6.10.3 Exploratory Analysis

INQoL questionnaire results will be presented in the by-subject listing only.

QMD Ref: Worldwide-TMP-ST-005-7.0 Effective: 12Aug2019	Governing QMD: Worldwide-SOP-ST-001
Confidentiality Statement	
This document is the property of Worldwide Clinical Trials Inc. and may not be duplicated, copied, altered or removed from company without prior approval from Worldwide Quality Assurance or in compliance with Worldwide Standard Operating Procedures.	

Worldwide Clinical Trials Controlled Quality Management Document		
 WORLDWIDE CLINICAL TRIALS	Sponsor:	PTC Therapeutics, Inc
	Protocol Number:	PTCEMF-GD-004
STATISTICAL ANALYSIS PLAN		

6.11 Pharmacokinetic Analyses

PK analyses will be discussed in a separate SAP.

6.12 Safety Analyses

The safety analyses will be presented for the Safety Population.

The adverse events and other safety summaries will be reported across all deflazacort treated periods. The adverse events occurred during placebo period for subject randomized to placebo under protocol version 3.0 will not be summarized and will only be included in by-subject listings.

